9.5. Statistical Analyses

The SAP will be finalized before database lock and it will include a more technical and detailed description of the statistical analyses described in this section. This section is a summary of the planned statistical analyses of the most important endpoints including primary and secondary endpoints.

9.5.1. General Considerations

The baseline value for study ARGX-113-1905 will be the value at the last visit in ARGX-113-1904.

All trial visits will be recalculated based on actual dates and will be referred to as "analysis visits" which will be used in the statistical analyses. The rules for calculating the analysis visits will be documented in the SAP. Rules for imputing partial dates or missing dates will also be documented in the SAP.

9.5.2. Participant Disposition

Participant disposition will be summarized in a table. It will include the number of participants enrolled previously on placebo and efgartigimod in ARGX-113-1904, who received IMP treatment, completed the trial, as well as the number of early discontinuations from IMP treatment and trial, with reasons for discontinuation from IMP or trial. Summaries will be provided for the overall trial period and, where relevant, by previous treatment group.

9.5.3. Analysis Sets and Protocol Deviations

The number of participants for the analysis set will be presented as described in Section 9.4.

Major protocol deviations, by previous treatment group in ARGX-113-1904, will be summarized in a table and presented in a listing.

9.5.4. Demographic and Baseline Characteristics, and Concomitant Medication

Participant demographic and baseline characteristic data, including prior and concomitant therapies will be summarized using standard summary statistics (Section 9.1) and listed.

9.5.5. **Primary Endpoint(s)**

Exposures to IMP and prednisone will be summarized. The safety analysis will be analyzed overall but also by status at entry into ARGX-113-1905.

Summaries of TEAEs and other safety parameters will be provided by treatment group. Summary statistics will be presented for all other safety endpoints including vital signs, physical examinations, laboratory values and ECGs.

AEs will be classified using the latest version of the MedDRA classification system. AEs and AESIs will be listed corresponding to SOC and MedDRA PT. Multiple occurrences of a single PT in a participant will be counted only once at the maximum severity/grade. Any AEs with missing severity or relationship to IMP will be classified as severe and treatment-related, respectively. All AEs will be summarized by relatedness to IMP. Any AEs leading to death or discontinuation of IMP will also be summarized. Clinically significant laboratory abnormalities will be summarized descriptively.

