- flare between DC and achieving CRmin that is not controlled by 2 dose levels of OCS above the dose at which the flare is observed and that is at least 0.3 mg/kg/day (Table 4)

In the absence of DC, participants will receive prednisone at the starting dose of 1.5 mg/kg/day. In case of uncontrolled flare before CRmin, participants will receive, as starting dose, the last dose from ARGX-113-1904. In case of flare after CRmin, participants will receive a prednisone dose in line with the severity of the flare, with the recommendation of a minimum of 0.3 mg/kg/day when the flare is of mild severity (PDAI activity score <15) and of 0.5 mg/kg/day when the flare is moderate to severe (PDAI activity score \geq 15). Dosing of efgartigimod PH20 SC will be done during on-site visits or home visits according to Table 2.

5. Participants who developed a prednisone-related SAE may prematurely roll over into ARGX-113-1905 and may be treated with efgartigimod PH20 SC through on-site or home visits according to the clinical statuses as described above. Concomitant prednisone will be considered to fit the clinical statuses as described above as far as compatible with the nature and severity of the SAE, with a lower dose to no concomitant prednisone being considered otherwise.

Participants or their caregivers (a person of legal age that the participant proposes to perform the administrations) may self-administer efgartigimod PH20 SC after they have successfully completed self-administration training (in ARGX-113-1904 with at least 1 refresher training in OLE trial ARGX-113-1905, or during ARGX-113-1905). All participants and/or their caregivers will receive a home guide for transport, storage, preparation, and administration of the IMP.

At any postbaseline visit before DC is achieved, the prednisone dose will be adjusted by incrementing dosage according to clinical judgment, with the recommendation to increase by 1 or more steps (Table 4) in case of disease progression or insufficient clinical change. To facilitate common judgments among investigators, recommendations for assessment of disease progression and insufficient clinical change are:

- Disease progression: increase of at least 5 in PDAI activity score compared to baseline score, observed at any postbaseline visit before DC

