## 5.1.3 Presentation of results

Unless mentioned otherwise tables will present TEAEs only.

The TEAE tables will be presented for the treatment and follow-up phase combined.

Tables to be produced for the topline results (see list of outputs in section 8.1) will be presented overall and by disease status at roll-over in 1905. These tables will show data for PV+PF participants as well as for PV participants.

_	SGS	Statistical Analysis Plan	
A	ARGX-113-1905	Final analysis	Final 1.0 of 26APR2024

An overview table will show the number and percentage of participants with at least one event, the incidence rate per 100 PYFU, the number of events and the event rate per 100 PYFU for the following:

- TEAEs
- Treatment related TEAEs
- Serious TEAEs
- Serious treatment related TEAEs
- Serious prednisone related TEAEs
- TEAEs of grade 3 or above
- Treatment-related TEAEs of grade 3 or above
- TEAEs related to prednisone
- TEAEs related to study procedures
- TEAEs for which the IMP was discontinued
- TEAEs for which the IMP was interrupted
- TEAEs of special interest
- Treatment related TEAEs of special interest
- TE IRR events
- Serious TE IRR events
- TE ISR events
- Fatal TEAEs

The overview table will be repeated specifically for ISR events, omitting the records related to TEAEs of special interest, prednisone-related TEAEs, IRR and ISR events.

A summary table by MedDRA system organ class and preferred term will show the number and percentage of participants with at least one event, the incidence rate per 100 PYFU, the number of events and the event rate per 100 PYFU. Each AE record in the clinical database is considered as a distinct adverse event and is counted as such.

The overview and summary tables mentioned above, will present:

- TEAEs
- post-TEAEs
- overall AEs (i.e., all AEs in the treatment + follow-up phase)

SGS	Statistical Analysis Plan	
ARGX-113-1905	Final analysis	Final 1.0 of 26APR2024

Separate tables will be prepared by MedDRA system organ class and preferred term showing the number and percentage of participants with at least one event, the incidence rate per 100 PYFU, the number of events and the event rate per 100 PYFU for the following:

- Most common TEAEs (>=5% in the Total group)
- Treatment related TEAEs
- Serious TEAEs
- Serious treatment related TEAEs
- Serious prednisone related TEAEs
- TEAEs of grade 3 or above
- Treatment-related TEAEs of grade 3 or above
- TEAEs related to prednisone
- TEAEs related to study procedures

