#### 5.2.3 Presentation of results

The statistical analysis will present results in standardized units, except for eGFR, which will be reported in mL/min/ $1.73m^2$ .

Continuous laboratory parameters will be summarized by means of descriptive statistics of the actual values and changes from baseline at each analysis visit. For albumin and LDL-C, also percent changes from baseline will be shown. Categorical parameters will be listed only.

Laboratory abnormalities will be presented as cross-tabulations of the abnormality at each post-baseline analysis visit and at the worst-case analysis visit versus the baseline abnormality. This table will also show numbers of participants with treatment-emergent abnormalities (see Definition of terms). The denominator for the percentage is the total number of participants per treatment and per analysis visit in

SGS	Statistical Analysis Plan	
ARGX-113-1905	Final analysis	Final 1.0 of 26APR2024

the Safety analysis set. Abnormalities will not be tabulated for those parameters for which toxicity grades are defined.

Laboratory toxicity grades will be presented as cross-tabulations of the toxicity at each post-baseline analysis visit and at the worst-case analysis visit versus the baseline toxicity. This table will also show numbers and cumulative numbers over decreasing toxicity grading of participants with treatment-emergent toxicities. The denominator for the percentage is the total number of participants per treatment and per analysis visit in the Safety analysis set. Parameters having toxicity grades defined in both directions (hypo and hyper) will be shown by direction.

Tables to be produced for the topline results (see list of outputs in section 8.1) will show data for PV+PF participants as well as for PV participants.

All laboratory data will be listed, but only for participants with any post-baseline abnormality/toxicity or clinically significant value.

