#### PHARMACODYNAMICS

-			
14.2.3.1	Descriptive Statistics of Actual Values, Changes from Baseline, Changes from 1904 Baseline and Changes from Treatment Period Baseline in Total IgG Level and IgG Subtype Levels by Visit	ROLL	
14.2.3.2	Descriptive Statistics of Actual Values, Percent Changes from Baseline, Percent Changes from 1904 Baseline and Percent Changes from Treatment Period Baseline in Total IgG Level and IgG Subtype Levels by Visit	ROLL	
14.2.3.3	Descriptive Statistics of Actual Values, Changes from Baseline, Changes from 1904 Baseline and Changes from Treatment Period Baseline in anti-Dsg-1/-3 antibodies by Visit	ROLL	
14.2.3.4	Descriptive Statistics of Actual Values, Percent Changes from Baseline, Percent Changes from 1904 Baseline and Percent Changes from Treatment Period Baseline in anti-Dsg-1/-3 antibodies by Visit	ROLL	TL
IMMMUNO	OGENICITY		
14.2.4.1	ADA: Anti-Drug Antibodies to Efgartigimod Sample Classification by Analysis Visit by Overall Anti-Drug Antibodies Participant Classification	SAF	
14.2.4.2	ADA: Anti-Drug Antibodies to Efgartigimod Participant Classification, Prevalence and Incidence	SAF	
14.2.4.3	NAb: Neutralizing Antibodies to Efgartigimod Sample Classification by Analysis Visit by Overall Neutralizing Antibodies Participant Classification	SAF	
14.2.4.4	NAb: Neutralizing Antibodies to Efgartigimod Participant Classification, Prevalence and Incidence	SAF	
14.2.4.5	NAb: Neutralizing Antibodies Positives to Efgartigimod Sample Classification by Overall Efgartigimod Anti-Drug Antibodies Participant Classification	SAF	
14.2.4.6	ADA: Descriptive Statistics of ADA Against Efgartigimod Titer Values by ADA Participant Classification Against Efgartigimod	SAF	
SAFETY			
ADVERSE	EVENTS		
14.3.1.1.1	Adverse Events Overview	SAF - ROLL	TL
14.3.1.1.2	Adverse Events Overview by Disease Status at Roll-over	SAF - ROLL	TL
14.3.1.2.1	Treatment-Emergent and Post-Treatment Adverse Events by MedDRA System Organ Class and Preferred Term	SAF - ROLL	TL
14.3.1.2.2	Treatment-Emergent and Post-Treatment Adverse Events by MedDRA System Organ Class and Preferred Term by Disease Status at Roll-over	SAF - ROLL	TL
14.3.1.2.3	Most Common (>=5% in the Total Group) Treatment-Emergent Adverse Events by MedDRA System Organ Class and Preferred Term	SAF	TL
14.3.1.3	Treatment Related Treatment-Emergent Adverse Events by MedDRA System Organ Class and Preferred Term	SAF	
	Page 62 of 84		

Page 62 of 84

System Version: 1.0, Status: Approved, Document ID: VV-TMF-172580

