_	SGS	Statistical Analysis Plan	
Al	RGX-113-1905	Final analysis	Final 1.0 of 26APR2024
•			

14.3.1.4.1	4.3.1.4.1 Serious Treatment-Emergent Adverse Events by MedDRA System Organ Class and Preferred Term		TL
14.3.1.4.2	Serious Treatment-Emergent Adverse Events by MedDRA System Organ Class and Preferred Term by Disease Status at Roll-over	SAF	TL
14.3.1.5	Serious Treatment Related Treatment-Emergent Adverse Events by MedDRA System Organ Class and Preferred Term	SAF	
14.3.1.6	Serious Prednisone Related Treatment-Emergent Adverse Events by MedDRA System Organ Class and Preferred Term	SAF	
14.3.1.7.1	Grade 3 or More Treatment-Emergent Adverse Events by MedDRA System Organ Class and Preferred Term	SAF	TL
14.3.1.7.2	Grade 3 or More Treatment-Emergent Adverse Events by MedDRA System Organ Class and Preferred Term by Disease Status at Roll- over	SAF	TL
14.3.1.8	Treatment Related Grade 3 or More Treatment-Emergent Adverse Events by MedDRA System Organ Class and Preferred Term	SAF	
14.3.1.9	Prednisone Related Treatment-Emergent Adverse Events by	SAF	

MedDRA System Organ Class and Preferred Term 14.3.1.10 Procedures Related Treatment-Emergent Adverse Events by SAF MedDRA System Organ Class and Preferred Term Treatment-Emergent Adverse Events Leading to Discontinuation of SAF 14.3.1.11.1 TL IMP by MedDRA System Organ Class and Preferred Term 14.3.1.11.2 Treatment-Emergent Adverse Events Leading to Discontinuation of TL SAF IMP by MedDRA System Organ Class and Preferred Term by Disease Status at Roll-over 14.3.1.12.1 Treatment-Emergent Adverse Events of Special Interest by SAF TL MedDRA System Organ Class and Preferred Term Treatment-Emergent Adverse Events of Special Interest by SAF 14.3.1.12.2 TL MedDRA System Organ Class and Preferred Term by Disease

	Status at Roll-over				
14.3.1.13	Treatment Related Treatment-Emergent Adverse Events of Special Interest by MedDRA System Organ Class and Preferred Term	SAF			
14.3.1.14	Treatment-Emergent Injection-Related Reactions by MedDRA System Organ Class and Preferred Term	SAF			
14.3.1.15	Serious Treatment-Emergent Injection-Related Reactions by MedDRA System Organ Class and Preferred Term	SAF			
14.3.1.16.1	Treatment-Emergent Injection Site Reactions - Overview	SAF	TL		
14.3.1.16.2	Treatment-Emergent Injection Site Reactions – Overview by Disease Status at Roll-over	SAF	TL		
14.3.1.16.3	Treatment-Emergent Injection Site Reactions by MedDRA System Organ Class and Preferred Term	SAF	TL		

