14.3.2.1 Descriptive Statistics of Laboratory Test Actual Values and SAF Changes from Baseline

SGS	Statistical Analysis Plan			
ARGX-113-190	95 Final analysis	Fir	nal 1.0 of 26	APR2024
14.3.2.2	Descriptive Statistics of Albumin and Low-Density Lipopro Cholesterol Actual Values and Changes from Baseline and Treatment Period Baseline	otein-	SAF	TL
14.3.2.3	Descriptive Statistics of Albumin and Low-Density Lipopro Cholesterol Actual Values and Percent Changes from Basel Treatment Period Baseline		SAF	TL
14.3.2.4	Cross-Tabulation of Laboratory Abnormalities Versus Baseline		SAF	
14.3.2.5	Cross-Tabulation of Laboratory Toxicity Grades Versus Ba	seline	SAF	
VITAL SIG	NS			
14.3.3.1	Descriptive Statistics of Vital Signs Actual Values and Char from Baseline	ıges	SAF	
14.3.3.2	Cross-Tabulation of Vital Signs Abnormalities Versus Base	line	SAF	
ECG				
14.3.4.1	Descriptive Statistics of ECG Actual Values and Changes fr Baseline	om	SAF	
14.3.4.2	Cross-Tabulation of ECG Abnormalities Versus Baseline		SAF	
14.3.4.3 Cross-Tabulation of QTCB/QTCF Abnormalities Versus Baseline		iseline	SAF	
14.3.4.4	Tabulation of QTc Change Abnormalities		SAF	

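### Protocol 9.5.5 promises safety results by entry status, but the SAP plans none of its 11 laboratory, vital-sign and ECG tables by status and does not record the change

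*Protocol*

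**What the plan says.** Protocol 9.5.5, on the primary endpoints, says: "The safety analysis will be analyzed overall but also by status at entry into ARGX-113-1905". It goes on: "Summary statistics will be presented for all other safety endpoints including vital signs, physical examinations, laboratory values and ECGs". Protocol Section 3 and 9.1.2 list these measures among the primary endpoints, next to adverse events.

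SAP 5.1.3 says that the topline AE tables "will be presented overall and by disease status at roll-over in 1905". SAP 5.2.3 says of the topline laboratory tables only that they "will show data for PV+PF participants as well as for PV participants". SAP 5.3.3 and 5.4.3 use the same wording for vital signs and ECGs. None of these three sections mentions disease status.

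SAP 2.5 defines disease status at roll-over in five categories: CRmin, CR, DC without CR, treatment failure, and flare after CRmin.

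Protocol 9.1.1 lets the SAP make minor changes of method without an amendment, provided they are documented there as changes from the protocol. SAP 6.1 is where that is done.

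**The concern.** The primary objective is the safety of treatment, extended treatment and retreatment, and entry status is how the protocol separates those situations. Status also governs exposure at the start of 1905. Protocol 4.1 (status 4) says "In the absence of DC, participants will receive prednisone at the starting dose of 1.5 mg/kg/day", gives flare entrants a recommended dose that depends on severity, and leaves CRmin entrants at 10 mg/day or less. Protocol Table 3 gives the higher initial efgartigimod regimen to treatment failures and to those starting a new cycle, but not to participants in DC or CR at roll-over.

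Disease status at roll-over is also an outcome of 1904, so its mix may differ between the two prior-treatment columns in SAP 2.4.2. Steroid-sensitive measures such as HbA1c, LDL-C and blood pressure could then differ between columns, or average out, because of the mix. No other planned summary fills the gap: C-GTI, which draws on HbA1c, blood pressure, LDL and BMI, is also overall only (SAP 4.1.3.7).

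**Working it through.** The plan has no sample-size, power or error-rate figure to reproduce. The check is a count of the planned tables and a comparison of the text.

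**1. Scope of the commitment.** The sentence in protocol 9.5.5 refers to the safety analysis without qualification. Two paragraphs in the same section cover AEs and the other safety measures, so it cannot be read as applying to AEs alone.

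**2. Count of the safety tables in SAP 8.1.**

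| Block | Tables | By disease status | Overall only, no by-status counterpart |
|---|---|---|---|
| Adverse events, 14.3.1.x | 26 | 8 | 10 |
| Laboratory, 14.3.2.1–5 | 5 | 0 | 5 |
| Vital signs, 14.3.3.1–2 | 2 | 0 | 2 |
| ECG, 14.3.4.1–4 | 4 | 0 | 4 |

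For AEs, 26 = 8 by status + 8 overall counterparts + 10 with no counterpart. The ten are 14.3.1.2.3, 14.3.1.3, 14.3.1.5, 14.3.1.6, 14.3.1.8, 14.3.1.9, 14.3.1.10, 14.3.1.13, 14.3.1.14 and 14.3.1.15. For laboratory, vital signs and ECG, 5 + 2 + 4 = 11, of which 0 are by status; "Cross-Tabulation of ECG Abnormalities Versus Baseline" (14.3.4.2) is typical. Physical examination is listed, not tabulated (SAP 5.5.2).

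**3. What the AE side still gives by status.** Table 14.3.1.1.2, "Adverse Events Overview by Disease Status at Roll-over", takes its rows from SAP 5.1.3. They include treatment-related, prednisone-related and serious prednisone-related events, each with participant counts, event counts and rates per 100 participant-years. Nine of the ten AE tables above have a row there. The tenth, 14.3.1.2.3 (most common events), is a subset of what 14.3.1.2.2 shows by status. What is missing for AEs is therefore the detailed breakdown, as in 14.3.1.6, "Serious Prednisone Related Treatment-Emergent Adverse Events by MedDRA System Organ Class and Preferred Term", and likewise 14.3.1.3 and 14.3.1.9.

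**4. Topline flags.** Tables 14.3.2.2 and 14.3.2.3 (albumin and LDL-C) are marked topline. Except for the most-common-events table 14.3.1.2.3, every overall AE table with that mark has a by-status version; these two do not.

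**5. Declared changes.** SAP 6.1 lists analysis visit labels, NCPD for different periods and the CRoff proportion. It does not mention safety by entry status.

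**6. Exposure by status.** Dose at entry is specified for some groups only: 1.5 mg/kg/day where DC is absent, and a recommended minimum of 0.3 or 0.5 mg/kg/day for flare after CRmin. Uncontrolled flare before CRmin carries over the last 1904 dose, for which no figure is given. Entrants after a prednisone-related SAE may have a lower dose or none. No dose is stated for CR entrants. The documents establish that exposure depends on status, but give no distribution of entry doses.

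**The case against.** The best defence is that protocol 9.4 and 9.5 leave detail to the SAP, the study tests no hypothesis, and comparisons between prior-treatment groups are purely descriptive (protocol 9.1.1). The SAP also plans prednisone exposure (NCPD and cumulative dose), baseline disease characteristics including prednisone dose, and IMP administration by status, so a reader will see any dose imbalance. This limits the harm. But seeing that doses differ does not show whether laboratory, vital-sign or ECG results differ, and leaving detail to the SAP does not cover silently dropping part of a stated analysis.

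A reader might infer that prednisone-related AEs are wholly pooled. They are not, as table 14.3.1.1.2 shows.

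A reader might also take a fold-difference in dose from protocol Table 4. At 70 kg the 1.5 mg/kg dose is 105 mg/day, which gives 105/35 = 3.0 against 0.5 mg/kg, 105/20 = 5.25 against 0.3 mg/kg and 105/10 = 10.5 against 10 mg/day. Over the 50 to 100 kg columns the ranges are 3.0–3.2, 3.75–5.5 and 7.5–15. The answer depends on the pair and the weight, and the last ratio sets a starting dose against an end-of-taper dose. CRmin and CRoff entrants, the group most clearly at 10 mg/day or less, join the safety set only if later dosed (SAP 2.1.1), and their roll-over-phase safety data are listed, not tabulated (SAP 2.4.3). None of these ratios describes the tables in question.

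Three further cautions stand. Participants who flare after CRmin in 1905 start a new cycle with the higher initial regimen, so later exposure crosses entry-status groups. No-DC entrants had already had at least 3 weeks at 1.5 mg/kg/day before the roll-over baseline, so the largest change from baseline need not be theirs. And by-visit tables split by status would be sparse.

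**Conclusion.** The gap between protocol and SAP is real. It covers all 11 laboratory, vital-sign and ECG tables. For AEs it is confined to detailed breakdowns whose totals are already given by status, or whose content is contained in a by-status table. It is undeclared in SAP 6.1. Followed as written, the SAP leaves part of a stated primary-endpoint analysis undone.

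The consequence for interpretation is a possibility, not a demonstrated bias. It assumes that status mix differs between columns and that the measures respond to the differing exposure; neither can be sized from the documents. No fold-difference in dose should be quoted. No hypothesis test is affected. The point should be settled before database lock but does not threaten the trial.

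**What to change.** In SAP 5.2.3, 5.3.3, 5.4.3 and list 8.1, add versions by disease status at roll-over, using the SAP 2.5 variable, of:

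- the worst-case rows of the abnormality and toxicity tables: 14.3.2.4, 14.3.2.5, 14.3.3.2 and 14.3.4.2 to 14.3.4.4;
- the topline albumin and LDL-C tables: 14.3.2.2 and 14.3.2.3.

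This covers 6 + 2 = 8 of the 11 tables. The worst-case restriction suits the first group only, because SAP 2.2.5 defines a worst-case visit for abnormalities and toxicity grades, not for change summaries. The other three (14.3.2.1, 14.3.3.1, 14.3.4.1) and the ten AE tables may stay overall only, but SAP 6.1 should then record each safety output deliberately kept that way, with the reason.

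The cost is repeat programming with an existing variable; SAP 2.4 already repeats every descriptive output by region. The downside is more pages and small cells. With at most about 213 participants (SAP 1.3) and five statuses, the average is no more than 213/5 = 42.6 per status before splitting by prior treatment, and fewer in the safety set. The by-visit albumin and LDL-C tables will be thinnest.
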